1.0 PROJECT TITLE

Trial of Improvisational Music Therapy's Effectiveness for Children with Autism (TIME-A): United Kingdom (UK) arm of the TIME-A study.

2.0 SUMMARY OF RESEARCH

TIME-A is a multi-centre international study of music therapy for children with Autism Spectrum Disorder (ASD) that has been funded by the Research Council of Norway. The international study is a three-arm, parallel group, researcher-blind, randomised trial testing the impact of music therapy plus enhanced treatment as usual versus enhanced treatment as usual alone over a 12 month period. Study participants are children aged from 4:0 to 6:11 years old, who have a clinical diagnosis of ASD, confirmed by independent assessment using validated diagnostic tools (the Autism Diagnostic Observation Schedule [1] and the Autism Diagnostic Interview-Revised [2]). Children who are already receiving music therapy or have done in the past will be excluded from the study, as will children with severe sensory impairment.

Study participants in the UK arm of the trial, which shall be funded by the NIHR HTA, will be recruited from NHS health services at six centres: Cambridge, Essex, Peterborough, and the London Boroughs of Hillingdon, Kensington & Chelsea and Westminster.

In keeping with the international study we will examine the impact of improvisational music therapy. This approach to delivering music therapy was originally developed in the UK [3]. It is the approach that is most widely used to deliver music therapy to children with autism in the NHS and has demonstrated efficacy in small scale trials [4,5]. All those in the trial will also receive enhanced treatment as usual: in addition to usual input from primary and secondary care, parents/ guardians will receive three counselling sessions delivered over a five month period. These sessions will be delivered by experienced clinicians who receive regular supervision and comprise psychoeducation, information about support organisations and support in coping with current problems in keeping with national guidelines [7]. In addition to this, those in one of the two active treatment arms of the trial will be offered either: low-intensity music therapy (weekly sessions for five months), or high-intensity music therapy (sessions three times a week for five months).

All music therapy sessions will last 30 minutes and be delivered by trained music therapists who have experience of working with children with ASD and are registered with the Health Care Professions Council. Therapists will deliver improvisational music therapy in accordance with consensus guidelines which have been developed from practice in previous studies [3-6]. To ensure treatment fidelity, therapists will be asked to document the content of sessions and video-record sessions. Notes from sessions will be used during monthly supervision and video-recordings will be monitored by the lead music therapist in the study.

At baseline eligibility will be established and the child's level of cognitive ability will be assessed using the Kaufman Assessment Battery for Children [10]. The primary outcome measure is the severity of autism symptoms using the social communication algorithm, which is derived from the ADOS [1]. This will be assessed by a trained researcher who is masked to allocation status. The measure has been selected because of its strong psychometric properties, including sensitivity to change [1], and because it has been widely used in other randomised trials of children with autism [11-13].

The main secondary outcomes are the Social Responsiveness Scale [14] - a carer based assessment of the severity of autism spectrum symptoms that has high inter-rater and test-retest reliability [15-16]. In addition to these outcomes which are being used across all centres in the international study, the UK-arm of the trial will include two additional items completed by parents/ guardians of children who take part in the study: the Short-Form

Parenting Stress index, a widely used and validated measure of difficulties in parent-child interactions [17], and the Warwick and Edinburgh Well Being Schedule, a short validated measure of mental well-being [33].

All outcome measures will be assessed 2, 5 and 12 months after randomisation, with the primary end-point being at 5 months.

The main data analysis will be conducted by statisticians based in the main centre in Norway. All primary analyses will be based on intention to treat. Descriptive analysis shall be performed to examine the distribution of each outcome in each group at baseline, at the end of intervention and the end of follow-up and differences in baseline variables between the two main comparison groups (music therapy plus enhanced treatment as usual versus enhanced treatment as usual alone). Following assessment of normality, treatment effects will be analysed using a generalized estimating equations (GEE) approach that allows for analysis of longitudinal data while accounting for correlation among repeated observations for each participant [32]. GEE analyses will also be used to examine dose-effect relationships and to explore effects of covariates including site, age and sub-types of ASD.

3.0 BACKGROUND AND RATIONALE

One in every 100 children in the UK has autism spectrum disorder (ASD) [19]. The core features of the condition are persistent impairment in reciprocal social interaction and social communication together with restricted, repetitive patterns of behaviour, interests or activities [41]. These features occur whether or not the person has intellectual disability and are typically present in early childhood. Developmental disabilities associated with ASD lead to poor health, social exclusion and reduced quality of life [20]. ASD is one of the most important causes of lifelong disability.

The evidence base to inform treatment of children with ASD and their families is weak [31]. Recent guidance from the National Institute for Health and Clinical Excellence concluded that psychotropic medication should not be used to manage its core features and emphasised advice, education and support for parents and efforts to adjust the child's environment to minimise the impact of their disabilities [7].

Over the last decade a number of small scale studies of improvisational music therapy have suggested that it has the potential to improve health and social outcomes of children with ASD. A Cochrane systematic review in 2010 identified three small randomised trials of music therapy and found evidence of improvements in verbal (Standardised Mean Difference = 0.36, 95% CI 0.15 to 0.57) and gestural (Standardised Mean Difference = 0.50, 95% CI 0.22 to 0.79) communication skills. Effects on behavioural problems were not statistically significant. On the basis of these findings the authors concluded that music therapy may help children with autistic spectrum disorder. However they highlighted differences in the approach to delivering music therapy in these trials compared to normal clinical practice. Most children receiving music therapy in clinical practice receive weekly sessions, but the trials tested more intensive, daily, sessions.

Since the publication of this review a number of observational studies have reported improvements in social communication in children with autism who were offered music therapy as it is delivered in the UK [27-30]. This approach involves therapists providing children with a range of musical instruments to play and using a range of techniques including making co-improvised music to engage the child in joint musical activities. During sessions the child is offered opportunities to develop and enhance their communication skills, including affect sharing, imitation, joint attention, and turn-taking, all of which are associated with later development in language and social competency [8,9]. Two subsequent

small-scale trials of weekly improvisational music therapy for children with ASD also found improvements in social communication during therapy [4,5].

With over 500 music therapists in the UK, many of whom work with children with ASD in the NHS, evidence is needed to ensure that this resource is used in the most effective manner. The TIME-A study has been designed to provide this evidence. It is sufficiently powered to generate important information about the clinical effectiveness of improvisational music therapy for children with autism spectrum disorders. A UK arm of this trial would help ensure that the main study achieves the required sample size and help enhance the generalizability of the study findings by including a substantial sub-group of participants who are recruited from NHS services in the UK.

Why this research is needed now?

In 2009 NIHR-Health Technology Appraisal issued a commissioned call for a randomised trial of music therapy for children with autism, however a project was not funded. Since then a number of new small-scale studies have highlighted the potential value of this approach to helping children with ASD [5, 27-30]. A systematic review of music therapy for children with autism, completed in 2010, concluded that 'music therapy may help children with autistic spectrum disorder to improve their communicative skills' and that 'more research is needed to examine whether the effects of music therapy are enduring' [6].

Recent guidance from the National Institute for Health and Clinical Excellence has stressed the importance of psychosocial approaches to helping children with autism and concluded that psychotropic medication should not be used to manage its core features 'because the balance of risks and benefits do not favour their use' [7]. However, the evidence base for psychosocial interventions for autism is weak [31], and a recent high-quality trial of parent-mediated communication skills found little evidence of benefit [11].

Last year a team of researchers in Norway obtained funding to set up a multi-centre international study of improvisational music therapy for children with autism aged between 4 and 7. The 'TIME-A study' will investigate the clinical effectiveness of the approach to music therapy which has been tested so far and is most widely used in the UK [32]. The team received funding to coordinate the study and start recruitment in a number of international sites, and is now looking to recruit participants in the UK.

Music therapy is widely offered to children with autism in the NHS, but the evidence base to support the use of this intervention is not strong enough to be confident that it represents an appropriate use of limited resources. A UK arm of the TIME-A study would help ensure that a high quality evaluation of this promising intervention is successfully completed and enhance the generalizability of the study findings by including a substantial sub-group of participants who are recruited from NHS services in the UK.

4.0 AIMS AND OBJECTIVES

The primary aim is to conduct a UK arm of an international multi-centre trial of music therapy for children with autism to ensure that the main trial recruits sufficient participants to be fully powered and to extend the generalizability of the trial findings to children and parents using NHS services in this country.

The study objectives are:

1) To determine whether improvisational music therapy in addition to enhanced treatment as usual is superior to enhanced treatment as usual alone in improving social communicative skills in children with ASD.

2) To examine whether improvisational music therapy in addition to enhanced treatment as usual is superior to enhanced treatment as usual alone in reducing stress and improving emotional well-being among parents/ guardians of children with ASD.

3) To explore whether any clinical benefits associated with adding improvisational music therapy to enhanced treatment as usual for children with ASD are influenced by the intensity of treatment that is offered.

4.0 STUDY HYPOTHESES

Primary hypothesis: Among children with autism spectrum disorder aged four to seven years old, adding 20 weeks of individual improvisational music therapy to enhanced treatment as usual will improve social communication measured at 5 months using the Autism Diagnostic Observation Schedule.

Secondary hypotheses:

i) Among children with autism spectrum disorder aged four to seven years old, adding 20 weeks of individual improvisational music therapy to enhanced treatment as usual will improve social communication at 12 months measured using the Autism Diagnostic Observation Schedule.

ii) Among children with autism spectrum disorder aged four to seven years old, adding 20 weeks of individual improvisational music therapy to enhanced treatment as usual will improve social communication judged by parents/ guardians and reduce levels of parental stress.

5.0 RESEARCH PLAN

5.1 Study design

A UK arm of a three arm, parallel group, researcher-blind, randomised multi-centre international trial which will examine the impact of adding music therapy to enhanced treatment as usual for children with Autism Spectrum Disorder over a 12-month period.

5.2 Target organisations

NHS services for children with Autism Spectrum Disorder in six areas of London and the south and east of England (Cambridge, Essex, Peterborough, and the London Boroughs of Hillingdon, Kensington & Chelsea and Westminster). NHS services for children in these areas include Child Development Centres and outpatient Child and Adolescent Mental Health Services. Services in these areas are provided by four large NHS Foundation Trusts: Cambridge and Peterborough NHS Foundation Trust, Central and North West London NHS Foundation Trust, Chelsea and Westminster Hospital NHS Foundation Trust and South Essex Partnership NHS Foundation Trust.

5.3 Patient care group

Children with Autism Spectrum Disorder and their parent/ guardians.

5.4 Recruitment

At each study centre information about the trial will be widely publicised among clinical colleagues working in Child Development Centres and outpatient Child and Adolescent Mental Health services. Members of the research team will present plans for the study at local academic and clinical meetings and continue to visit teams on a regular basis to remind

them about the study. Parents or guardians (referred to as parents in the remainder of this proposal) of children aged 4:00 to 6:11 years who have a clinical diagnosis of Autism Spectrum Disorder will be approached by a staff member, given basic information about the study and asked to provide verbal consent to be contacted by a local researcher.

5.5 Obtaining consent

Parents who agree to meet a member of the study team will be invited to a meeting. At this meeting the parent will be provided with written and verbal information about the study including a copy of the Patient Information Sheet. The researcher will encourage parents of potential participants to spend as much time as they want asking questions about the study and considering whether they and their child want to take part. In all instances potential participants will have at least 24 hours before deciding whether they wish to take part in the study. Before any trial specific procedures are performed, the parent will need to sign and date an Informed Consent Form. Following this, the researcher will assess eligibility to participate and collect baseline clinical and demographic data. Those who are ineligible will be thanked for their time and informed of the reason(s) for this. The process of obtaining informed consent will be conducted in accordance with the requirements of Research Ethics Committee guidance and Good Clinical Practice.

5.6 Randomisation

Researchers at each site will enter the results of the baseline assessment on a web-based Case Report Form. Remote web-based randomisation will be undertaken through a fully automated service operated by Uni Research (Norway). The allocation ratio for the study is 2:1:1 such that equal numbers of participants are allocated to enhanced treatment as usual and music therapy and, among those allocated to music therapy, equal numbers will be allocated to high and low-intensity treatment. Randomisation will be made in blocks, with block size randomly assigned to between four and eight. Following randomisation the UK-based trial coordinator will be informed which arm of the trial the participant has been assigned to. Parents and therapists will then be given information about allocation status and arrangements made for delivering parent counselling sessions. For those in one of the two active arms of the trial, arrangements will also be made for delivering music therapy sessions. Study researchers are based in separate departments to those involved in organising treatment, helping to ensure they remain masked to the allocation status of study participants.

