11.3 Sample size calculation for the main trial

A total sample of 300 needs to be recruited in the study as a whole. Previous trials of improvisational music therapy for children with ASD have reported medium effect sizes associated with active intervention. A Cochrane review of music therapy for children with ASD calculated a Standardised Mean Difference of 0.50 for gestural communication skills and 0.36 for verbal communication skills [6].

A sample of 235 patients will provide 90% power to detect a medium effect size of the intervention on the social communication scale of the ADOS score at 12 months with a 5% level of statistical significance [32]. To take account of possible clustering at the level of study therapists and study centres and a drop out we have inflated the total sample required to 300. Loss to follow-up in trials of psychosocial intervention for children with autism spectrum disorder tends to be low. The PACT trial of parent mediated communication focused treatment reported a follow-up rate of 96% at 13 months [11].

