11.5 Rate of recruitment

The aim is to recruit 100 participants over a 12 month period. With the support of Clinical Studies Officers from the Mental Health Research Network, two full-time researchers one covering sites in London, the other covering sites in Cambridge and Essex, will each aim to recruit 50 participants during this period. Previous research among children with autism suggests that meetings need to be arranged with eight parents/ families for every five children that will take part in the trial [11], which means that each researcher will need to meet with an average 1.6 parent/ families each week. Data from recruitment sites indicate that the numbers of children they assess each year who have autism spectrum disorder and are within this age group are well in excess of this (see section 10 above).

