16.2 Dissemination of the results of the UK-arm of the trial

We will prepare a full report to NIHR: HTA that will detail the results of the UK arm of the TIME-A trial and place these in the context of findings from the international study. These findings will provide the basis for a paper on the process and outcomes of the UK arm of the TIME-A study. We will also prepare an English version of the treatment guidelines for improvisational music therapy as used in the main study which will be made freely available to all those working in the NHS.

We will present findings from the UK arm of the trial in the context of the international study at local and national meetings. At a local level we will convene a seminar open to the study team and participants to discuss study findings. At a national level we will present the findings of the study at the National Autistic Society's professional conference and the annual meeting of the British Association of Music Therapists.

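### Section 5.6 does not tie the random blocks to site and site is only exploratory in the analysis; chance imbalance by site and UK rater then costs some precision, without bias

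*Protocol*

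**What the plan says.** Protocol section 5.6 gives the randomisation. "Remote web-based randomisation will be undertaken through a fully automated service"; "The allocation ratio for the study is 2:1:1"; and "Randomisation will be made in blocks, with block size randomly assigned to between four and eight". Neither this section nor any other names a stratification factor.

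Sections 2.0 and 13.0 plan generalised estimating equations (GEE) and list site among the covariates or possible confounders to be explored. Neither makes site a term of the primary treatment comparison.

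Section 11.3 raises the sample from 235 to 300 for dropout and for "possible clustering at the level of study therapists and study centres". It gives no intraclass correlation (ICC).

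In the UK, children "will be recruited from NHS health services at six centres" (section 2.0). Section 11.5 sets a UK target of 100 and relies on "two full-time researchers one covering sites in London, the other covering sites in Cambridge and Essex", with 50 children each. Section 21.2 gives the same two researchers the lead in assessment and follow-up. Section 16.2 promises a report to the funder "that will detail the results of the UK arm of the TIME-A trial".

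**The concern.** Differences between centres or raters drop out of a treatment contrast when the arms are balanced within centre and rater, or when the model fits that factor. The protocol secures neither. Blocks tied to nothing balance the arms over the whole run of allocations, not inside a site, and an exploratory look at site does not fix it in the primary model.

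The protocol's own facts make this worth settling. It allows extra children for possible centre clustering. The primary outcome is an observer-rated ADOS score, and in the UK the observer largely coincides with the region. A UK-only result on 100 children will also be reported, and chance imbalance weighs more there than in the full 300. What is at stake is some precision, and the balance of the arms within sites and raters.

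**Working it through.** **Inputs from the protocol.** Ratio 2:1:1, so 1:1 for control against pooled music therapy; 300 children in all, 100 in the UK; six UK sites; two researchers with 50 children each; 96% follow-up in the trial cited in 11.3, so 300 × 0.96 = 288 analysed.

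**Assumptions.** One unstratified sequence; UK children falling at random places in it; equal site sizes (16 or 17 in the UK); ten equal sites internationally; centre ICC 0.01 to 0.10. Block sizes are 4 or 8, the only sizes from four to eight that hold 2:1:1 exactly.

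**The plan's own figure.** The protocol states no imbalance, ICC or design effect to reproduce. The 235 in 11.3 corresponds to an effect of 2 × (1.960 + 1.282)/√235 = 0.42 SD (two-sided 5%, 90% power). The protocol gives no planning value to compare with this, and nothing below depends on it.

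**Step 1: imbalance.** For m children out of a nearly balanced 300, the number allocated music therapy has SD = √[m × 0.25 × (300 − m)/299].

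| Group | SD | 95% range |
|---|---|---|
| UK, m = 100 | √16.7 = 4.1 | 42 to 58 |
| One researcher's region, m = 50 | √10.5 = 3.2 | 19 to 31 |
| One site, m = 17 | √4.0 = 2.0 | 5 to 12 |

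A simulation of 20,000 sequences gives the same SDs and ranges. A second simulation (3,000 runs per scenario, one sequence over the 100 UK children) finds at least one of six sites split 65:35 or worse in about 53% of trials. With blocks drawn within site this falls to 0%. The mean difference between arms falls from 3.0 to 0.8 children per site and, with blocks drawn within researcher, from 4.0 to 0.8 per researcher.

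**Step 2: effect on the unadjusted contrast.** The mean shift is zero in every scenario. Its SD, in outcome SD units:

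| Centre ICC | Six UK sites, no strata | Six UK sites, blocks within site | Ten sites, N = 300, no strata |
|---|---|---|---|
| 0.01 | 0.019 | 0.005 | 0.011 |
| 0.05 | 0.040 | 0.011 | 0.024 |
| 0.10 | 0.057 | 0.015 | 0.035 |

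The standard error of the contrast is about 2/√100 = 0.20 for the UK and 2/√300 = 0.115 overall. At ICC 0.05 the UK shift is (0.040/0.20)² = 4% of the variance.

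For raters, the difference between arms in the share of children from one region has SD 0.10 and an absolute 95th percentile of 0.20. If the two raters differ by 0.3 to 0.5 SD (assumed), about 5% of trials would see a shift above 0.20 × 0.3 = 0.06 to 0.20 × 0.5 = 0.10 SD. This applies to a contrast of follow-up scores without adjustment, so it is an upper figure for the planned analysis of change.

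**Step 3: precision.** Removing centre variance gains 1/(1 − ICC) − 1. That is 2.0%, 5.3% or 11.1% at ICC 0.02, 0.05 or 0.10, worth about 6, 15 or 32 of 288 children.

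To separate the two steps, note that fitting k sites after unstratified allocation loses about (k − 1)/N: 9/300 = 3% for ten sites, 5/100 = 5% for six UK sites, 1/100 = 1% for two regions. Simulated efficiencies, without and with stratification, agree: 0.969 and 0.998 (ten sites, 288 children), 0.951 and 0.996 (six UK sites), 0.990 and 0.999 (two regions). Dividing the ten-site figures by (1 − ICC) gives information relative to an unadjusted, unstratified analysis:

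| Centre ICC | Fit site only | Stratify and fit site |
|---|---|---|
| 0.02 | 0.969/0.98 = 0.99 | 0.998/0.98 = 1.02 |
| 0.05 | 0.969/0.95 = 1.02 | 0.998/0.95 = 1.05 |
| 0.10 | 0.969/0.90 = 1.08 | 0.998/0.90 = 1.11 |

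Stratification adds about 3% whatever the ICC. At ICC 0.10 most of the gain comes from the site term; at 0.02 the site term alone roughly breaks even.

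**The case against.** The strongest reply is that section 5.6 is silent on strata and does not deny them. A central automated service could hold a list per site, section 7.0 says the UK arm follows the main trial's basic methods, and the analysis plan may fit site. A reader might infer that the trial is known to run one sequence that ignores site; the document does not show that. What stands against the reply is that stratification has to be fixed before the first child is allocated, so it belongs in 5.6, and that exploratory is the status 13.0 actually gives to site.

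A reader might also infer that centre or rater differences bias the result. They do not: the expected shift is zero. Section 13.0 compares changes from baseline, so a stable difference between a strict and a lenient rater largely subtracts out. The exception is a child whose recent earlier ADOS is reused as baseline, which section 12.1 permits. This part of the objection stands in full.

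Nor should the whole 2 to 11% be credited to stratified blocks, since at the higher ICCs most of it comes from fitting site. And section 11.3 calls clustering possible, which is weaker than saying that the sponsor expects it.

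Finally, the service is run from Norway for an international trial already funded to recruit elsewhere (sections 3.0 and 5.6), so the UK team may not control the setting alone. That is fair, and it bears on the cost of the change.

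**Conclusion.** The point holds as a modest matter of balance and precision. The stated method neither blocks by site nor commits to a site term, although the protocol itself allows for centre clustering and UK rater and region largely coincide. Followed as written, sizeable imbalance at small UK sites is likely, and imbalance by researcher is possible but smaller.

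The cost is noise that is small against a UK standard error of about 0.20 SD. Stratification is worth roughly 3% of information for ten assumed sites and about 5% for six UK sites, given a fitted site term. These sizes rest on equal sites, an assumed number of international sites and assumed ICCs. They also rest on there being no site lists in the randomisation service, which the protocol leaves open. The validity of the treatment comparison is not in question.

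**What to change.** In section 5.6, state that the random-length blocks, of size 4 or 8, are drawn separately within each site, or within researcher region (London; Cambridge and Essex) where sites are very small. If the service already does this, the change is only to say so.

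In section 13.0, make the same factor a pre-specified term of the primary treatment model instead of an exploratory covariate.

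If allocation has already begun without strata, stratify the remaining children and keep the site term for all.

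The cost is a setting in the web service, to be agreed with the coordinating centre, and a sentence in each of the two sections. No extra children or staff are needed. The downside is more incomplete blocks and slightly more predictable allocation at small sites, limited by the random block length and central allocation.
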